**Figure 1: Study Design for KPL-301-C203**

A Safety Review Committee (SRC) including 2 physicians from the Sponsor, 1 physician from the Sponsor's contract research organization (CRO), and 1 independent physician who is an expert in critical care medicine, pulmonary disorders, infectious diseases and/or COVID-19 treatment (SRC Chairperson) will meet periodically to review AEs/SAEs, reasons for study discontinuations, and key clinical and laboratory assessments. SRC activities will be guided by an SRC Charter. The initial SRC meeting will be triggered once the initial 4 subjects have completed Day 8. SRC members will be blinded to subject treatment assignment.

A Data Monitoring Committee (DMC) has been established by the Sponsor to conduct periodic reviews and may meet more frequently as needed to review unblinded safety data from the Phase 2 and 3 portions of the study. The initial meeting will be triggered at 1 month after the first subject is enrolled. The DMC charter will detail the composition, roles and responsibilities and analysis plan for the DMC's activities.

The study may be terminated if unexpected, significant, or unacceptable safety risks to enrolled subjects arise, or if recommended by applicable board(s) after review of safety data.

## 6.2. Number of Subjects (planned)

A total of approximately 836 subjects will be enrolled in this study. Approximately 171 subjects will be randomized to the Phase 2 part, and approximately 665 subjects will be randomized to the Phase 3 part.

In Phase 2:

- Cohort 1: Approximately 120 non-ventilated subjects, and
- Cohort 2: Approximately 51 ventilated subjects

In Phase 3:

- Cohort 1: Approximately 600 non-ventilated subjects, and

Cohort 2: Approximately 117 ventilated subjects (approximately 65 subjects at time of enrollment closure)

### **6.3. Treatment Assignment**

Across the two study parts (Phase 2 and Phase 3), approximately 836 subjects will be randomized in a 1:1:1 allocation ratio to receive a mavrilimumab (10 mg/kg or 6 mg/kg) or placebo. No subject will receive more than one dose.

Details regarding randomization to treatment are provided in Section 8.4.1.

### **6.4. Dose Adjustment Criteria**

Mavrilimumab will be administered as a single IV infusion over 60 minutes. No dose adjustments are planned.

#### **6.4.1. Safety Criteria for Adjustment or Stopping Doses**

At any time during the infusion of study drug, should a moderate reaction occur, the infusion will be stopped for a period of at least 30 minutes and restarted at the Investigator's discretion only after the events have resolved. The infusion rate should be re-started at a rate tolerated by the subject. Infusions must be completed within 4 hours of study drug preparation (see Pharmacy Manual for more details). Should a severe reaction occur, the infusion will be stopped permanently. Severity of infusion reactions are to be determined by the Investigator. No dose adjustments are planned. Additional details regarding study drug dosing are provided in Section 9.5.

### **6.5. Criteria for Study Termination**

The study may be terminated or temporarily suspended in whole or in part by the Sponsor at any time. Reasons for such action include:

- Unexpected, significant, or unacceptable safety risk to subjects enrolled in the study
- Decision based on recommendations from applicable board(s) after review of safety and/or efficacy data
- Discontinuation of the study drug development program by the Sponsor

The Investigator may be informed of additional procedures to be followed in order to ensure that adequate consideration is given to the protection of the subject's interests. The Investigator or Sponsor, depending on the local regulation, will be responsible for informing the Institutional Review Board (IRB) of the early termination of the trial.

## 7. SELECTION CRITERIA AND WITHDRAWAL OF SUBJECTS

### 7.1. Subject Inclusion Criteria

Subjects must meet all the following inclusion criteria to be eligible for enrollment in the study.

1. Subject (or legally authorized representative) is able and willing to provide informed consent, which includes compliance with study requirements and restrictions listed in the consent form. Consent must be performed per institutional regulations.
2. Age of  $\geq 18$  years
3. Positive SARS-CoV-2 (2019-nCoV) test within 14 days prior to randomization
4. Hospitalized for SARS-CoV-2 (2019-nCoV)
5. Bilateral pneumonia on chest x-ray or CT
6. *[Original Criteria Deleted]*
7. At least one of the following, within 7 days prior to randomization:
  - Ferritin  $> 500$  ng/mL
  - CRP  $> 5$  mg/dL
  - D-dimer  $> 1,000$  ng/mL
  - LDH  $> 250$  U/L
  - Fever - a measured temperature of at least 100.4°F [38°C]
8. For Cohort 1: Receiving any form of non-invasive ventilation OR oxygenation to maintain  $SpO_2 \geq 92\%$  and non-mechanically ventilated (examples include nasal cannula, face mask, venturi mask, high-flow nasal cannula, and NIV or non-invasive positive pressure ventilation)
9. For Cohort 2: Recently ventilated with mechanical ventilation beginning within 48 hours prior to randomization
10. Female subjects must be:
  - postmenopausal, defined as at least 12 months post cessation of menses (without an alternative medical cause), or
  - permanently sterile following documented hysterectomy, bilateral salpingectomy, bilateral oophorectomy, or tubal ligation or having a male partner with vasectomy as affirmed by the subject, or
  - nonpregnant, nonlactating, and if sexually active having agreed to use a highly effective method of contraception (ie, hormonal contraceptives associated with inhibition of ovulation or intrauterine device [IUD], or intrauterine hormone-releasing system [IUS], or sexual abstinence) from Screening Visit until Day 90.
11. Male subjects must have documented vasectomy or if sexually active must agree to use a highly effective method of contraception with their partners of childbearing potential (ie, hormonal contraceptives associated with the inhibition of ovulation or IUD, or IUS, or

sexual abstinence) from Screening until Day 90. Male subjects must agree to refrain from donating sperm during this time period.

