## 7.2. Subject Exclusion Criteria

Subjects who meet any of the following exclusion criteria will not be eligible for study enrollment.

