#### 12.1.5.1. Pregnancy Screen

All pre-menopausal women who are not surgically sterile will have a urine or serum pregnancy test performed at Screening. Pregnancy testing is not required for post-menopausal women. For female subjects of childbearing potential who are discharged and return to the site later, a pregnancy test must be repeated at the last visit the subject completes on the study.

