### 12.5.1. Pregnancy Reporting

Formal reproduction toxicology testing of KPL-301 has not yet been performed.

Female subjects of childbearing potential must therefore agree to use a highly effective and protocol-approved contraceptive method (Section 7.1) for the duration of the study (until Day 90), which is 90 days after dosing and covers 5 ½ half-lives of mavrilimumab (approximately 15 days). Regular pregnancy tests will be performed for female subjects of childbearing potential, as defined in the Schedule of Activities (Table 2).

Male subjects who have a female partner of childbearing potential must agree to use a highly effective and protocol approved contraceptive method (Section 7.1) for the duration of the study and until 16 weeks after last study drug administration under this protocol.

If a subject becomes pregnant while participating in the study, study drug dosing must be discontinued immediately.

A female subject must immediately inform the Investigator if she becomes pregnant during the study. A male subject must inform the Investigator if his female partner becomes pregnant during the study. Pregnancies occurring up to 16 weeks after last study drug administration must be reported to the Investigator. The Investigator must report all pregnancies to the Sponsor or designee immediately and no later than 24 hours of their first knowledge of the pregnancy. The Investigator should counsel the subject that it is unknown what effects study drug might have on a fetus. Monitoring of the subject should continue until conclusion of the pregnancy. The newborn should be monitored for a minimum of 6 months after birth, or longer as per local requirement.

Instances of fetal death or congenital abnormality, if brought to the attention of the Investigator at any time after cessation of the study treatment and considered by the Investigator to be possibly related to the study treatment, must be reported to the Sponsor as an SAE.

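### Inclusion criterion 10 requires a woman to be neither pregnant nor breastfeeding in only one of its three alternatives, so some pregnant or breastfeeding women meet it as written

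*Combined protocol and SAP*

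**What the plan says.** Criterion 10 in Section 7.1 opens "Female subjects must be" and then gives three bullets. The first two end in the word or, so meeting any one is enough.

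- Bullet 1: "postmenopausal, defined as at least 12 months post cessation of menses (without an alternative medical cause), or"
- Bullet 2 is for women who are permanently sterile after one of four listed procedures. It closes "or tubal ligation or having a male partner with vasectomy as affirmed by the subject, or"
- Bullet 3 begins "nonpregnant, nonlactating, and if sexually active having agreed to use a highly effective method of contraception" and then lists the accepted methods.

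The Synopsis repeats this structure.

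Three other sections bear on the point. Section 12.1.5.1 says: "All pre-menopausal women who are not surgically sterile will have a urine or serum pregnancy test performed at Screening". Section 12.5.1 says: "Formal reproduction toxicology testing of KPL-301 has not yet been performed". It then continues: "Female subjects of childbearing potential must therefore agree to use a highly effective and protocol-approved contraceptive method (Section 7.1"). Section 4 lists reproductive toxicity among the important potential risks that will continue to be monitored.

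**The concern.** The condition on pregnancy and lactation belongs to one alternative, not to the criterion as a whole. A woman who enters through bullet 2 never reaches it. Bullet 2 also includes a woman whose partner has had a vasectomy, although she is not sterile herself.

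What is at stake is the safety of a fetus or a breastfed infant. The protocol treats fetal risk as unknown: Section 12.5.1 acknowledges the missing toxicology, and Section 16.3 requires women of childbearing potential to be told of unknown risks to a fetus. An eligibility rule that a site can apply correctly and still admit such a woman does not fit those provisions. It also leaves the screening pregnancy test without a decisive role for some of the women who take it.

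**Working it through.** No figure is involved, so the check is a reading of the rule. The criterion is met if bullet 1 or bullet 2 or bullet 3 is met.

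**Step 1. Apply the rule to each case.** All the women below are premenopausal. Bullet 1 leaves no evident gap, because its definition rules out absence of menses with another medical cause.

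| Case | Bullet 2 | Bullet 3 | Criterion 10 |
|---|---|---|---|
| Breastfeeding, tubal ligation | met | not met | met |
| Breastfeeding, partner with vasectomy | met | not met | met |
| Pregnant, partner with vasectomy (for example, done after conception) | met | not met | met |
| Pregnant, tubal ligation | doubtful | not met | doubtful |
| Pregnant or breastfeeding, no listed procedure, no partner vasectomy | not met | not met | not met |

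The partner-vasectomy limb has to be read as separate from the words about permanent sterility. A partner's operation cannot make the woman sterile, so on any other reading no woman could meet the limb and it would do nothing.

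**Step 2. Look for a backstop in the exclusions.** Section 7.2 says: "Subjects who meet any of the following exclusion criteria will not be eligible for study enrollment". The list has 17 numbers, of which 7, 9, 13 and 14 are deleted, leaving 17 − 4 = 13 in force. None names pregnancy or lactation. Criterion 5 concerns serious illness and does not naturally describe either state.

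**Step 3. Look for a backstop in the screening test.** Under Section 12.1.5.1 a woman relying on a partner's vasectomy is tested, since she is neither postmenopausal nor surgically sterile. A woman with a tubal ligation is probably not tested, if that counts as surgical sterility. For neither group does Section 12.1.5.1, Table 2 or Table 4 say that a positive result excludes. By contrast, the protocol states outright that a positive tuberculosis result is exclusionary where testing is required. No section schedules a question or check on lactation.

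**Step 4. Look for a backstop after entry.** Section 12.5.1 has a rule for a subject who becomes pregnant during the study. It does not address one already pregnant at entry.

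Nothing in steps 2 to 4 reverses the first three rows of the table.

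**The case against.** The best counter-argument is that the intent is clear. The protocol schedules pregnancy tests, requires contraception, warns of fetal risk at consent and sets up pregnancy reporting. Most investigators would not enrol a pregnant woman, whatever the bullets say. Inclusion criterion 1 also makes compliance with restrictions in the consent form a condition of entry, and the consent form was not available for this review, so a restriction there cannot be ruled out. The intent is probably as described. Even so, eligibility should follow from the stated criteria, and a consent-form restriction is only a possibility.

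Four stronger readings are tempting, and the documents do not support them.

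- A reader might infer that pregnancy after tubal ligation also passes. Bullet 2 requires permanent sterility, and a pregnant woman is hard to describe that way. It is not a clear case.
- A reader might infer that Section 12.5.1 flatly contradicts criterion 10, because partner vasectomy is absent from the method list in bullet 3. But Section 12.5.1 points to Section 7.1 as a whole, where partner vasectomy does appear in bullet 2. The conflict is arguable only.
- A reader might infer that every such enrolment exposes a fetus or infant. Allocation is 1:1:1, so one in three receives placebo and two in three receive active drug. The documents do not address transfer into milk or whether breastfeeding continues in hospital. Section 4 adds that several of the listed risks lack a biological rationale after a single dose, without saying which.
- A reader might infer that an amendment would still protect many women here. Sections 1.2 and 1.4 of the Phase 3 SAP report enrolment closed at 581 subjects in Cohort 1 and 63 in Cohort 2.

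**Conclusion.** The point stands as a gap in an eligibility rule with a safety consequence. As written, criterion 10 admits a breastfeeding woman with a tubal ligation or a vasectomised partner, and a pregnant woman with a vasectomised partner. No exclusion criterion and no stated consequence of the screening test turns her away. This sits against the protocol's own account of reproductive risk.

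The size cannot be computed, because the documents give no count of women in these groups; it is likely small. A case may involve exposure, but need not. With enrolment reported closed, the prospective effect in this trial is limited, although the text remains wrong for any further use of the criterion. There is no effect on sample size, power, type I error or the analysis.

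The conclusion rests on two assumptions: that the bullets are true alternatives, as their wording says, and that no removed page carries a separate exclusion. It does not imply that such women were enrolled or that the sponsor meant to enrol them.

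**What to change.** Reconcile criterion 10 in the Synopsis and Section 7.1 with Sections 12.1.5.1 and 12.5.1:

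1. Take the existing condition of being neither pregnant nor breastfeeding out of bullet 3 and place it ahead of the list, so that it applies whichever bullet a woman meets.
2. Remove partner vasectomy from the bullet on permanent sterility, and state its status once, consistently with the method list and with Section 12.5.1.
3. State one eligibility consequence for the screening pregnancy test, and make clear whether women with a tubal ligation are tested.

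The cost is a short redraft in two places, matching edits to the two later sections, and a line on the eligibility form. The pregnancy test is already scheduled for women relying on a partner's vasectomy, but lactation status would have to be asked at Screening, which the protocol does not now provide for. A very few women would become ineligible. Since enrolment is reported closed, the redraft mainly serves any reopening or reuse of the criterion.

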## 7.2. Subject Exclusion Criteria

Subjects who meet any of the following exclusion criteria will not be eligible for study enrollment.

### General Exclusion Criteria

1. Onset of COVID-19 symptoms > 14 days prior to randomization
2. Hospitalized > 7 days prior to randomization
3. [For Cohort 1 only] Need for invasive mechanical ventilation
4. Need for ECMO
5. Serious prior or concomitant illness that in the opinion of the Investigator precludes the subject from enrolling in the trial, including (but not limited to):
  - History of pulmonary alveolar proteinosis
  - Severe and uncontrolled pulmonary disease other than COVID-19 pneumonia (eg, asthma, chronic obstructive pulmonary disease, or others)
  - Pre-existing (prior to development of COVID-19) severe left ventricular systolic dysfunction (ie, left ventricular ejection fraction < 35%)
  - Hemodynamic instability with pressor requirements of norepinephrine at a dose of > 0.5 mcg/kg/min or equivalent (total if multiple pressors used) for more than 12 hours continuously, myocardial infarction, stroke, and cardiogenic septic shock within 30 days prior to randomization
  - Known active tuberculosis (TB) determined by history and local standard of care, or history of incompletely treated TB or at high risk for latent TB (exposure or prior incarceration)
    - If tuberculosis testing is required per local regulations, one positive (or two indeterminate) interferon gamma release assay test results or one positive polymerase chain reaction test is exclusionary
  - Concomitant uncontrolled systemic bacterial or fungal infection
  - Concomitant respiratory viral infection other than COVID-19 and influenza that, in the opinion of the Investigator, represents a higher mortality risk (eg, SARS, Middle East respiratory syndrome [MERS])
6. Recent treatment with cell-depleting biological therapies (eg, anti-CD20) within 12 months, non-cell-depleting biological therapies (such as anti-tumor necrosis factor [TNF], anakinra, anti-IL-6 receptor [eg, tocilizumab], or abatacept) within 8 weeks (or 5 half-lives, whichever is longer), treatment with alkylating agents within 12 weeks, treatment with cyclosporine A, azathioprine, cyclophosphamide, mycophenolate mofetil (MMF), or other immunosuppressant (except for corticosteroids) within 4 weeks prior to

randomization. Medications that become standard of care for COVID-19 and/or receive emergency use authorization may be allowed after discussion with the medical monitor.

7. *[Original Criteria Deleted]*

8. If subject is receiving or has received hydroxychloroquine within 3 months prior to randomization, a corrected QT interval by Fridericia's method (QTcF) on Screening electrocardiogram (ECG) of  $\geq 500$ ms is exclusionary. If subject has a pacemaker, this criterion does not apply.

9. *[Original Criteria Deleted]*

10. Enrolled in another investigational study of a medical intervention within 30 days prior to randomization. Participation in open label trials involving investigational treatments for COVID-19 may be allowed upon approval by the Sponsor.

11. Known hypersensitivity to mavrilimumab or any of its excipients

12. In the opinion of the Investigator, unable to comply with the requirements to participate in the study

13. *[Original Criteria Deleted]*

14. *[Original Criteria Deleted]*

15. At Screening blood tests, any of the following:

- Aspartate transaminase (AST)  $> 10 \times$  upper limit of normal (ULN)
- Alanine transaminase (ALT)  $> 10 \times$  ULN
- Hemoglobin  $< 7.5$  g/dL
- Neutrophils  $< 1,500/\text{mm}^3$
- Absolute platelet count  $< 50,000/\text{mm}^3$
- Creatinine clearance  $< 30$  mL/min (by Cockcroft-Gault formula) (Cockcroft DW, 1976)

16. Life expectancy less than 48 hours, in the opinion of the Investigator

17. Known human immunodeficiency virus infection (regardless of immunological status), known hepatitis B virus surface antigen positivity and/or anti-hepatitis C virus positivity

### 7.3. **Withdrawal of Subjects**

#### 7.3.1. **Treatment Stopping Criteria**

Should a moderate reaction occur during infusion of the study drug, the infusion will be stopped and restarted at the Investigator's discretion after the events have resolved. Should a severe reaction occur, the infusion will be permanently discontinued, but subjects will continue their participation in the study. Such severe reactions include, but are not limited to, urticaria, hypersensitivity, hypotension, bradycardia, hypoxia, generalized rash, or a change in mental status. If four (4) causally related severe reactions with 24-hour of dosing occur, study enrollment will be paused until the DMC can review the cases and determine if there is an

adverse drug-related safety signal. Details regarding study drug dosing are provided in Section 9.5.

#### **7.3.2. Replacement policy**

No subject replacement will be done, regardless of the reason for study discontinuation.

#### **7.3.3. Withdrawal of informed consent**

Subjects may voluntarily withdraw consent to participate in the study for any reason at any time. Withdrawal of consent occurs only when a subject:

- Does not want to participate in the study anymore,
- AND
- Does not allow further collection of personal data.

It is encouraged that the subject provides withdrawal of consent in writing.

In this situation, the Investigator should make a reasonable effort (eg, telephone call, e-mail, letter) to understand the primary reason for the subject's decision to withdraw his/her consent and record this information. The subject's vital status can be verified upon contact with subject's primary care physician or other sources according to local rules and regulations.

No further assessments must be conducted, and the data that would have been collected at subsequent visits will be considered missing.

Further attempts to contact the subject are not allowed unless safety findings require communication or follow-up.

All efforts should be made to complete the assessments prior to study withdrawal. A final evaluation at the time of the subject's study withdrawal should be made as detailed in the assessment table (Table 2).

The Sponsor will continue to keep and use collected study information (including any data resulting from the analysis of a subject's samples until the time of withdrawal) according to applicable law.

All biological samples not yet analyzed at the time of withdrawal may still be used for further testing/analysis in accordance with the terms of this protocol and the informed consent form and with local rules and regulations.

#### **7.3.4. Lost to follow-up**

For subjects whose status is unclear because they fail to complete study visits without stating an intention to discontinue or withdraw, the Investigator must show "due diligence" by documenting in the source documents the steps taken to contact the subject, eg, dates of telephone calls, registered letters. A subject should not be considered as lost to follow-up until the end of the study when due diligence has been completed.

